### **8.3.6. Cardiovascular and Death Events**

Not Applicable.

### **8.3.7. Disease-Related Events and/or Disease-Related Outcomes Not Qualifying as AEs or SAEs**

Not Applicable.

### **8.3.8. Adverse Events of Special Interest**

Not applicable.

#### **8.3.8.1. Lack of Efficacy**

This section is not applicable because efficacy is not expected in the study population.

### **8.3.9. Medical Device Deficiencies**

Not Applicable.

### **8.3.10. Medication Errors**

Medication errors may result from the administration or consumption of the study intervention by the wrong participant, or at the wrong time, or at the wrong dosage strength.

Exposures to the study intervention under study may occur in clinical trial settings, such as medication errors.

Safety Event	Recorded on the DCT	Reported on the CT SAE Report Form to Pfizer Safety Within 24 Hours of Awareness
Medication errors	All (regardless of whether associated with an AE)	Only if associated with an SAE

Medication errors include:

- Medication errors involving participant exposure to the study intervention;
- Potential medication errors or uses outside of what is foreseen in the protocol that do or do not involve the study participant.

Other examples include, but are not limited to:

- The administration of expired study intervention;
- The administration of an incorrect study intervention;
- The administration of an incorrect dosage;

- The administration of study intervention that has undergone temperature excursion from the specified storage range, unless it is determined by the sponsor that the study intervention under question is acceptable for use.

Such medication errors occurring to a study participant are to be captured on the medication error page of the DCT, which is a specific version of the AE page.

In the event of a medication dosing error, the sponsor should be notified within 24 hours.

Whether or not the medication error is accompanied by an AE, as determined by the investigator, the medication error is recorded on the medication error page of the DCT and, if applicable, any associated AE(s), serious and nonserious, are recorded on the AE page of the DCT.

Medication errors should be reported to Pfizer Safety within 24 hours on a CT SAE Report Form **only when associated with an SAE**.

#### **8.4. Pharmacokinetics**

##### **8.4.1. Plasma for Analysis of Abrocitinib and Metabolites**

Blood samples of approximately 6 mL, to provide approximately 3 mL of plasma will be collected into appropriately labeled tubes containing K2EDTA for measurement of plasma concentrations of abrocitinib and its metabolites PF-06471658/M1, PF-07055087/M2, and PF-07054874/M4 as specified in the CCI [REDACTED]

Instructions for the collection and handling of biological samples will be provided in the laboratory manual or by the sponsor. The actual date and time (24-hour clock time) of each sample will be recorded.

The actual times may change, but the number of samples will remain the same. All efforts will be made to obtain the samples at the exact nominal time relative to dosing. Collection of samples up to and including 10 hours after dose administration that are obtained within 10% of the nominal time (eg, within 6 minutes of a 60-minute sample) relative to dosing will not be captured as a protocol deviation, as long as the exact time of the collection is noted on the source document and data collection tool (eg, DCT). Collection of samples more than 10 hours after dose administration that are obtained  $\leq$ 1 hour away from the nominal time relative to dosing will not be captured as a protocol deviation, as long as the exact time of the collection is noted on the source document and data collection tool (eg, DCT).

[figure not shown]
[figure not shown]
Plasma samples will be analyzed using validated analytical methods in compliance with applicable SOPs.

CCI [REDACTED]

[REDACTED]

[REDACTED]

CCI

CCI

## **8.6. Biomarkers**

Biomarkers are not evaluated in this study.

## **8.7. Immunogenicity Assessments**

Immunogenicity assessments are not included in this study.

## **8.8. Health Economics**

Health economics/medical resource utilization and health economics parameters are not evaluated in this study.

## **9. STATISTICAL CONSIDERATIONS**

Detailed methodology for summary and statistical analyses of the data collected in this study is outlined here and further detailed in an SAP, which will be maintained by the sponsor. The SAP may modify what is outlined in the protocol where appropriate; however, any major modifications of the primary endpoint definitions or their analyses will also be reflected in a protocol amendment.

### **9.1. Statistical Hypotheses**

No formal inferential statistics will be applied to the safety data.

## 9.2. Analysis Sets

For purposes of analysis, the following analysis sets are defined:

Participant Analysis Set	Description
Enrolled	All participants who sign the ICD.
Randomly assigned to study intervention	Participants will be randomized to 1 of 6 treatment sequences in a 3-way crossover with 3-period design. In Part A, a total of 18 healthy participants will be enrolled in the study so that 3 participants will be enrolled in each treatment sequence.
PK Population	The PK concentration population is defined as all enrolled participants who received at least 1 dose of abrocitinib and in whom at least 1 plasma concentration value is reported.
Taste	All participants who receive at least 1 abrocitinib oral suspension formulation for taste evaluation and complete the abrocitinib Taste Assessment Questionnaire.
Safety	All participants randomly assigned to study intervention and who take at least 1 dose of study intervention. Participants will be analyzed according to the product they actually received.

## 9.3. Statistical Analyses

The SAP will be developed and finalized before database lock and will describe the participant populations to be included in the analyses, and procedures for accounting for missing, unused, and spurious data. This section is a summary of the planned statistical analyses of the primary and secondary endpoints.

### 9.3.1. Safety Analyses

All safety analyses will be performed on the safety population.

AEs, ECGs, BP, pulse rate, and safety laboratory data will be reviewed and summarized on an ongoing basis during the study to evaluate the safety of participants. Any clinical laboratory, ECG, BP, and pulse rate abnormalities of potential clinical concern will be described. Safety data will be presented in tabular and/or graphical format and summarized descriptively, where appropriate.

CCI

Medical history and physical examination information, as applicable, collected during the course of the study will be considered source data and will not be required to be reported, unless otherwise noted. However, any untoward findings identified on physical examinations conducted during the active collection period will be captured as AEs, if those findings meet the definition of an AE. Data collected at screening that are used for inclusion/exclusion criteria, such as laboratory data, ECGs, and vital signs, will be considered source data, and will not be required to be reported, unless otherwise noted. Demographic data collected at screening will be reported.

All safety analyses will be performed on the safety population.

### **9.3.1.1. Electrocardiogram Analyses**

Changes from baseline for the ECG parameters QT interval, heart rate, QTc interval, PR interval, and QRS complex will be summarized by treatment and time.

The number (%) of participants with maximum postdose QTc values and maximum increases from baseline in the following categories will be tabulated by treatment (Table 7):

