**Table 1. Schedule of Activities (Part A)**

Visit Identifier a Abbreviations used in this table may be found in Appendix 9: Abbreviations	Screening b	Period 1				Periods 2			Period 3			Early Termination/ DC
		Day -28 to Day -2	Day -1	Day 1	Day 2	Day 3	Day 1	Day 2	Day 3	Day 1	Day 2	
Informed consent	X											
CRU confinement		X	→	→	→	→	→	→	→	→	→	X
Inclusion/exclusion criteria	X	X										
Medical, drug, tobacco and alcohol history	X	X										
Physical examination d	X	X									X	X
Height and weight assessment	X											
Safety laboratory e	X	X										X
Demography (including height and weight)	X											
Pregnancy test for WOCBP only	X	X										X
Contraception check for WOCBP only	X	X										X
Serum FSH in post-menopausal females f	X											
Urine drug testing	X	X										
Single 12-Lead ECG	X		X g									X
Supine BP, pulse rate, and oral temperature	X		X h									X
Serology: HBcAb, HBsAg, HBsAb, HCVAb, HIV tests i	X											
QuantiFERON ® - TB Gold Test j	X											
COVID-19 questionnaire k	X	X										
COVID-19 testing l	X	X				X						
COVID-19 check temperature m	X	X	X	X	X	X	X	X	X	X	X	
Study treatment administration n			X		X	X	X	X	X	X	X	
CCI				X	X	X	X	X	X	X	X	

PFIZER CONFIDENTIAL

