**Table 1. Schedule of Activities (Part A)**

Visit Identifier a Abbreviations used in this table may be found in Appendix 9: Abbreviations	Screening b	Period 1				Periods 2			Period 3			Early Termination/ DC
Days Relative to Day 1	Day -28 to Day -2	Day -1	Day 1	Day 2	Day 3	Day 1	Day 2	Day 3	Day 1	Day 2	Day 3 c	
CCI												
CRU discharge												X
Serious and nonserious AE monitoring	X	X	→	→	→	→	→	→	→	→	→	→
Prior/concomitant treatments	X	X	→	→	→	→	→	→	→	→	→	→

- a. Day relative to the first day of study intervention dosing in all periods.
- b. Screening must take place a maximum of 28 days prior to the administration of the study intervention in Period 1.
- c. Day 3 of Period 3 in Part A of the study overlaps with Day -1 of Period 4 in Part B of the study.
- d. A complete physical examination will be done at screening or may be deferred to Day -1 of Period 1 at the discretion of the investigator. A complete physical examination would also be performed at the Early Termination/DC visit (if this occurs). A brief physical examination would be performed at Day 3 of Period 3 and could be performed at other times if findings during the previous examination or new/open AE, at the discretion of the investigator.
- e. Safety laboratory assessments must be collected following at least a 4-hour fasting. For details on the tests to be performed, please refer to protocol [Appendix 2](#). The hematology, urinalysis, and clinical chemistry tests will be performed at screening, each admission to the CRU, at Day -1 of Period 4 in Part B, at study discharge, and early withdrawal. Samples will be collected if the reason for DC is related to an AE. Additional assessments may be performed at the discretion of the investigator.
- f. Females who are amenorrheic  $\geq$ 12 consecutive months only.
- g. To be collected at predose of abrocitinib.
- h. To be collected at predose and 1-hour postdose (around  $T_{max}$ ) of abrocitinib.
- i. HBsAb tested as reflex test only in participants who are HBsAg negative but are HBcAb positive.
- j. QuantiFERON test to be performed at screening. Prior QuantiFERON test is acceptable when performed within the 12 weeks prior to Day 1 of Period 1.
- k. Check exposure to positive participant, residence or travel in area of high incidence and COVID-19 related signs and symptoms. To be done at each visit.

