**Table 2. Schedule of Activities (Part B)**

Visit Identifier a Abbreviations used in this table may be found in Appendix 9: Abbreviations	Period 4		Period 5	Period 6	Period 7	Period 8	Period 9		Early Termination/ DC	Follow-up b
Days Relative to Day 1	Day -1 c	Day 1	Day 1	Day 1	Day 1	Day 1	Day 1	Day 2		28-35 Days

- a. Day relative to the first day of study intervention dosing in all periods.
- b. Contact may occur via telephone contact and must occur 28 to 35 days from administration of the final dose of study intervention, either in Parts A (in case of early termination/DC) or in Part B of the study.
- c. Day -1 of Period 4 in Part B of the study overlaps with Day 3 of Period 3 in Part A of the study.
- d. For new participants enrolled in Part B only, all Screening and Day -1 visit procedures will be performed as listed in [Table 1](#) SoA (Part A).
- e. A complete physical examination will be done at screening or may be deferred to Day -1 of Period 4 at the discretion of the investigator for new participants admitting for Part B only of the study. A complete physical examination should be performed on Day 2 of Period 9 or at the Early Termination/DC visit (if this occurs). A brief physical examination can be performed at other times if findings during the previous examination or new/open AE, at the discretion of the investigator.
- f. Section 8.2.4 Safety laboratory test assessments consist of hematology, urinalysis, and clinical chemistry. For details on the tests to be performed, please refer to protocol [Appendix 2](#). The safety tests will be performed at screening, Day-1 of Period 4, each admission to CRU, at study discharge, and early withdrawal. All assessments must be collected following at least a 4-hour fasting period. Samples will be collected if the reason for DC is related to an AE. Additional assessments may be performed at the discretion of the investigator.
- g. To be collected at predose of abrocitinib for new participants enrolled in Part B only.
- h. To be collected at predose and 1-hour postdose (around  $T_{max}$ ) of abrocitinib.
- i. For new participants joining this part of the study, and admitted for residence, a subsequent COVID-19 test will be performed after 4 days (ie, upon completion of  $4 \times 24$  hours in-house), or if they develop COVID-19 like symptom(s).
- j. To be done at least daily during residence.

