**Table 7. Safety QTc Assessment**

Degree of Prolongation	Mild (msec)	Moderate (msec)	Severe (msec)
Absolute value	>450-480	>480-500	>500
Increase from baseline		30-60	>60

In addition, the number of participants with uncorrected QT values >500 msec will be summarized.

CCI

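### Does the protocol's by-treatment QTc table have to be formally withdrawn, given that the schedule provides only one routine postdose ECG per completer?

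*Protocol*

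**What the plan says.** Protocol section 9.3.1.1 plans three ECG outputs:

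- Changes from baseline in QT, heart rate and the other intervals: "QTc interval, PR interval, and QRS complex will be summarized by treatment and time".
- The Table 7 categories, for which "maximum postdose QTc values and maximum increases from baseline in the following categories will be tabulated by treatment".
- A count described as "the number of participants with uncorrected QT values" above 500 msec, with no split by treatment stated.

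The 12-lead ECG is part of a secondary safety endpoint (protocol section 3).

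Collection is set by the row "Single 12-Lead ECG" in the schedule of activities. In Table 1 (Part A) it is marked at Screening, Period 1 Day 1 and Early Termination/DC. Footnote g says of the Period 1 reading: "To be collected at predose of abrocitinib". In Table 2 (Part B) it is marked at Period 4 Day 1, Period 9 Day 2 and Early Termination/DC. Footnote g there reads: "To be collected at predose of abrocitinib for new participants enrolled in Part B only". Vital signs are handled differently. Footnote h says: "To be collected at predose and 1-hour postdose".

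In the SAP, section 8.3.7 states only that ECG data are listed to sponsor standards. Section 6.2 includes ECG results among the data types for standard safety summaries, and section 8.3 promises summary tables by treatment and by study part without naming ECG. Protocol section 9 allows the SAP to modify the protocol's analyses and asks for an amendment only when a primary endpoint or its analysis changes in a major way.

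**The concern.** A summary by treatment and time, and a maximum over postdose values, both presuppose several postdose ECGs under each treatment. The schedule does not supply them. Read literally, the protocol commits the sponsor to a QTc table whose Part A rows have no routine data and whose other rows hold a handful of participants with a single reading each, taken the day after dosing. Vital signs have a reading 1 hour after the dose, close to the time of peak concentration; the ECG has none.

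The SAP could have settled the matter by saying that the table is dropped, but it does not, and two of its general statements could be taken to promise ECG summaries. At stake is the reporting of a secondary safety endpoint: a reader might take a nearly empty table as evidence that no formulation affects QTc.

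**Working it through.** The documents state no ECG count, so there is no figure to reproduce. The check is a count from the schedule and the sequence tables, followed by a comparison of the governing texts.

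**Are the column positions reliable?** Some other schedule rows look shifted in the extracted text, so the ECG columns were checked against the physical-examination row, whose visits are also given in words. In Table 1 that row is marked at Period 3 Day 3 and at Early Termination/DC. Footnote d confirms this: "A brief physical examination would be performed at Day 3 of Period 3". In Table 2 the physical-examination marks fall in the same two columns as the later ECG marks (Period 9 Day 2 and Early Termination/DC), and footnote e names those two visits. The predose restrictions come from footnote text and do not depend on columns.

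**Routine postdose ECGs.** Assume 18 participants complete both parts, 3 per sequence, and leave out early-termination and unscheduled ECGs.

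- Doses per completer: 3 + 6 = 9. Routine postdose ECGs: 1.
- Part A: 18 × 3 = 54 doses, 0 postdose ECGs.
- Part B: 18 × 6 = 108 doses, 18 postdose ECGs.
- Overall: 18 / (54 + 108) = 18 / 162 = 11.1%.

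**Which treatments the 18 readings follow** (Period 9 column of protocol Table 5):

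| Sequence | Period 9 treatment | Participants with one reading |
|---|---|---|
| 1 | F6+ARA | 3 |
| 2 | F5+ARA | 3 |
| 3 | F4+ARA | 3 |
| 4 | F3 | 3 |
| 5 | F2 | 3 |
| 6 | F1 | 3 |

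If some Part B participants are new, these counts do not change, because every Part B completer has the Period 9 Day 2 ECG.

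**Treatment groups without a routine postdose ECG**, by how treatment is grouped:

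- Three Part A treatments plus six formulations with and without famotidine: 3 + 12 = 15 groups, 15 − 6 = 9 empty.
- Famotidine pooled in Part B: 3 + 6 = 9 groups, 9 − 6 = 3 empty.
- Tablet plus six formulations across both parts: 7 groups, 7 − 6 = 1 empty (the tablet).

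The share therefore depends on the grouping, but on each of these groupings the scheduled data are too thin for a by-treatment QTc display.

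**What will the analyst produce?**

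- SAP 8.3.7 is specific to ECG and says that the data are listed. SAP 8.3.5 and 8.3.6 say the same for laboratory data and vital signs, so listing is the SAP's consistent choice for measured safety data.
- SAP 8.3 speaks of tables by treatment in general terms. It has content without ECG: discontinuation counts (8.3.1 and 8.3.3) and adverse events (8.3.4) are all to be given by treatment.
- SAP 6.2 is a general list of safety data types and specifies no ECG table.
- ECG is not a primary endpoint, so under protocol section 9 the SAP may replace the 9.3.1.1 outputs without an amendment.

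The specific text governs the general text, and the result is an ECG listing.

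**The case for a change.** The strongest case for a change is that 9.3.1.1 is a specific commitment about a stated secondary endpoint, and a specific commitment should be withdrawn in words, not by silence. A programmer who reads SAP 6.2 and 8.3 alongside 9.3.1.1 could reasonably build Table 7. That table would have no routine data for Treatments A, B and C and 3 participants in each Period 9 group, and a casual reader could mistake it for reassurance. The remedy would be wording only.

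Part of this stands. The SAP does not say that Table 7 is replaced, and the ECG data cannot support comparisons of QTc between formulations or near peak exposure.

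The consequence is smaller than it looks. The Part A rows need not be empty in practice: Table 1 has an ECG at Early Termination/DC, and the protocol foresees participants who complete Part A only. Nor is a maximum without meaning: with one reading it is that reading, and protocol section 8.2.3 requires repeat ECGs once a QTc or QT threshold is crossed, so the participants who matter most for the table's upper categories would have several values. These extra readings do not arise systematically by treatment, but they would all appear in the listing. If Table 7 were built, its denominators would show how little it rests on.

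**Conclusion.** The mismatch is real, but it calls for no change. Scheduled data give 0 postdose ECGs for 54 Part A doses and 18 for 108 Part B doses, so the 9.3.1.1 displays cannot be filled in any useful way. The SAP's operative ECG text has already moved to a listing, as the protocol permits for a non-primary analysis. Stating that the table is dropped would be tidy, but it would alter no estimate, no primary result and no safety procedure. This is a gap that an analyst fills sensibly by following SAP 8.3.7.

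The counts assume that all 18 participants complete both parts, that the ECG rows are aligned as the physical-examination check indicates, and that early-termination, repeat and unscheduled ECGs are left out. The reading of the SAP assumes that its ECG-specific section prevails over its general safety statements. Some text near Table 7 and elsewhere in SAP section 8.3 is blacked out, but both ECG rows, section 9.3.1.1 and SAP 8.3.7 are legible, so the conclusion does not depend on hidden text.

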**Table 7. Safety QTc Assessment**

Degree of Prolongation	Mild (msec)	Moderate (msec)	Severe (msec)
Absolute value	>450-480	>480-500	>500
Increase from baseline		30-60	>60

In addition, the number of participants with uncorrected QT values >500 msec will be summarized.

CCI

### **9.3.2.1. Pharmacokinetic Analyses**

#### **9.3.2.1.1. Analysis of Population**

The PK concentration population is defined as all participants randomized and treated who have at least 1 concentration in at least 1 treatment period.

The PK parameter analysis population is defined as all participants randomized and treated who have at least 1 of the PK parameters of primary interest in at least 1 treatment period.

### 9.3.2.1.2. Derivation of Pharmacokinetic Parameters Prior to Analysis

PK parameters for abrocitinib will be derived from the plasma concentrationtime profiles as shown in Table 8.

**Table 8. Derivation of PK Parameters**

Parameter	Definition	Method of Determination
AUC 24	Area under the plasma concentration-time profile from time 0 to 24 hours	Linear/Log trapezoidal method.
AUC last	Area under the plasma concentration-time profile from time 0 to the time of the last quantifiable concentration (C last )	Linear/Log trapezoidal method.
AUC inf a	Area under the plasma concentration-time profile from time 0 extrapolated to infinity	AUC last + (C last * / k el ), where C last * is the predicted plasma concentration at the last quantifiable time point estimated from the log-linear regression analysis.
C max	Maximum plasma concentration	Observed directly from data.
T max	Time for C max	Observed directly from data as time of first occurrence.
t 1/2 a	Terminal elimination half-life	Log e (2)/k el , where k el is the terminal phase rate constant calculated by a linear regression of the log-linear concentration-time curve. Only those data points judged to describe the terminal log-linear decline will be used in the regression.

a. If data permit.

Actual PK sampling times will be used in the derivation of PK parameters.

PK parameters in Table 8 will be summarized descriptively by analyte and by treatment, as applicable, in accordance with Pfizer Data Standards. Concentrations will be listed and summarized descriptively by analyte, nominal PK sampling time and treatment. Individual participant and median profiles of the plasma concentration-time data will be plotted by treatment using actual and nominal times, respectively. Median profiles will be presented on both linear-linear and log-linear scales.

For the rBA portion of Part A, natural log transformed Abrocitinib AUCinf (if data permit), AUClast and Cmax will be analyzed using a mixed effect model with sequence, period and treatment as fixed effects and participant within sequence as a random effect. Estimates of the adjusted mean differences (Test-Reference) and corresponding 90% CIs will be obtained from the model. The adjusted mean differences and 90% CIs for the differences will be exponentiated to provide estimates of the ratio of adjusted geometric means (Test/Reference) and 90% CIs for the ratios. Treatment A (Abrocitinib tablet) is the Reference Treatment

[figure not shown]
while Treatment B (Abrocitinib suspension) and Treatment C (Abrocitinib tablet + famotidine) are the Test Treatments.

For the taste assessment in Part B of the study, the data used in the analysis will be transcribed and rescaled to a score from 0 to 100 from the raw measurements on the questionnaire. The sensory attributes (overall liking, mouthfeel, bitterness, sourness, saltiness, tongue/mouth burn) from the taste questionnaires ([Appendix 8](#)) will be listed and descriptively summarized by prototype formulation, and question across participants. Summary statistics (mean and 90% CI) will be calculated for the various questions. Radar plots for each of 4 time points, summarizing all attributes for each treatment will be generated. Boxplots of each attribute will be plotted against the time points.

[figure not shown]
[figure not shown]
[figure not shown]

